8.2 Off Study Criteria

- a) Death.
- b) Lost to follow-up.
- c) Patient enrollment onto another COG study with tumor therapeutic intent (eg, at recurrence).
- d) Withdrawal of consent for any further data submission.
- e) The fifth anniversary of the date the patient was enrolled on this study.
- f) Patient did not receive protocol treatment after study enrollment.

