The historical data from the COG trial ACNS0122 shows that for the 102 patients with localized NGGCT, all failures have occurred within two years of initiating treatment with a single exception of a patient who failed at approximately six years post initiation of treatment. In fact, most failures occurred within one year of initiating treatment. As indicated above, the outcome for the subset of 49 patients treated on ACNS0122 who would have been eligible for treatment on ACNS1123 is exceptional with only three failures in the first year and one in the second year of follow up. Thirty-eight patients have been followed for more than three years. With so few failures in the historical data, the usual time-to-event distributions, exponential, Weibull etc., are difficult to characterize and to assess for adequacy of fit; so the Study Committee has no estimate of a hazard rate and clearly no estimate of median progression-free survival. The binomial distribution appeared to be the best distribution on which to design this trial reflecting the fact that with rare exception all failures are expected to occur early. The binomial distribution parameterized by the 3-year PFS rate is expected to be sufficient to capture virtually all failures and reflects the fact that the investigators are confident that all patients will be successfully followed for at least three years. This method requires that no patient be lost to follow up within the first three years. All patients who fail to be evaluated for progression at the 3-year mark will be included in the primary analysis as failures. The Principal Investigators are committed that no patient be lost to follow up within three years of initiating treatment.

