Considering the current results of ACNS0122, a true, unknown 3-year PFS rate of 0.82 for this reduced therapy approach is considered unacceptable by the study team. The sample size calculation will be based on the binomial distribution testing that the true, unknown 3-year PFS rate is at most 82% (null hypothesis: ≤ 0.82) and powered to detect that the 3-year PFS rate is really 93% (0.93). East 5.3[©] was used to calculate the require sample size of 77 patients. This design will reject the null hypothesis if at least 69 patients (≥ 69) are progression free after three years and conclude that reduced therapy is acceptable. Due to the discrete distribution, the actual type I error rate is 0.0492 (probability of falsely concluding that the treatment is effective when the true 3-year PFS rate is 0.82) and statistical power is 0.911 (probability of correctly concluding that the treatment is effective when the true 3-year PFS rate is 0.93).

In order for the reduced therapy approach to be considered to have sufficient merit for continued investigation, our design requires a statistically significant result – p -value < 0.0492. The null hypothesis must be rejected otherwise this approach will have to be reconsidered.

Due to the expected accrual rate, expected low failure rate and three year PFS endpoint, even one interim analysis for futility that would stop accrual early is not feasible. Note that interim analyses would be restricted to patients who are documented failures within three years of initiation of treatment and those patients followed for three years failure free. Thus, no formal futility interim analysis is planned. However, if 9 patients are documented to have failed (progressed or lost to follow up) before three years of follow up and fewer than 77 patients eligible for the primary analysis have begun treatment, accrual will be suspended until the COG Data Safety Monitoring Board (DSMB) has had the opportunity to review all data.

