disease that would be required to address the primary study objective with statistical confidence even though considerable effort will be required to assure that no patient is lost to follow up within three years of initiating treatment. The study team is confident that this is possible.

In order for the reduced therapy approach to be considered to have sufficient merit for continued investigation, the null hypothesis must be rejected otherwise this approach will have to be reconsidered.

Due to the expected accrual rate, expected low failure rate and 3-year PFS endpoint, even one interim analysis for futility that would stop accrual early is not practical. If at any point in the trial, 7 patients are documented to have failed (progressed or been lost to follow up) before three years of follow up and fewer than 79 patients eligible for the primary analysis have begun treatment, accrual will be suspended until the COG DSMB has had the opportunity to review all data.

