15.12 Patterns of Failure Evaluation

The patterns of failure for patients with localized CNS GCT may be described as local, ventricular, distant or a combination of local, ventricular, and/or and distant and are based primarily on imaging evaluation of the neuraxis. Local failure is defined as progression of known residual tumor or the appearance of tumor at known prior sites of disease that were at some point without evidence of disease. Ventricular failure is defined as the appearance of tumor at sites within the ventricular system other than known prior sites of disease. Distant failure is defined as the appearance of tumor at sites outside the ventricles or the primary tumor volume. Distant failure most often occurs in the subarachnoid space and may occur at any point within the neuraxis. Although rare, extra-CNS metastasis represents distant failure. Combined local, ventricular, and/or distant failure is defined when evaluation of the entire neuraxis reveals failure at two or three of the defined categories. The monitoring of EFS will assess the rate of failure. Determining the patterns of failure will require an assessment of tumor recurrence with respect to targeting and dosimetry.

There is no universally accepted analytical method to assess pattern of failure. For this study, the pattern of failure will be assessed qualitatively and quantitatively by registering MR data obtained at the time of failure to the dosimetry from the original treatment plan.

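### The accrual-suspension triggers (9 and 7 failures) sit at the limits of the primary tests but do not name death without progression or withdrawal of consent, which those tests count as failures

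*Combined protocol and SAP*

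**What the plan says.** **Primary analysis.** Sections 9.3.1 and 9.3.2 each test a three-year PFS rate with an exact binomial rule and share one sentence on missing evaluations: "All patients who fail to be evaluated for progression at the 3-year mark will be included in the primary analysis as failures". No reason for the missing evaluation is excepted.

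**Suspension trigger.** No futility analysis is planned. Instead, Stratum 1 accrual is suspended for board review "if 9 patients are documented to have failed (progressed or lost to follow up) before three years of follow up", provided fewer than 77 patients eligible for the primary analysis have begun treatment. Stratum 2 is suspended if "7 patients are documented to have failed (progressed or been lost to follow up) before three years of follow up", provided fewer than 79 have begun.

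**Off-study categories.** Section 8.2 lists death (a), loss to follow-up (b) and "Withdrawal of consent for any further data submission" (d) as separate items.

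**Who is in the test.** Section 9.1 restricts the primary analysis in each stratum to eligible patients who received the reduced radiotherapy. Stratum 1 patients must also be evaluable on their response to induction.

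**Other oversight.** Section 12.2 has the data and safety monitoring committee reviewing interim toxicity and outcome reports, with power to recommend modification or termination.

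**The concern.** The trigger has a clear purpose: once enough failures have occurred that the null hypothesis cannot be rejected, no more children should start reduced irradiation until the board has looked. That works only if the trigger and the test count the same patients.

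A patient who dies without progression before three years cannot be evaluated for progression at three years, so the test counts a failure. The same holds for a patient who withdraws consent for further data. The trigger's parenthesis names neither. I found no definition of a PFS event in the protocol that would bring death into it, and Section 8.2 separates both events from loss to follow-up.

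With no futility analysis, this is the only numerical rule in either stratum that suspends accrual on progression outcomes. If it undercounts, accrual can continue after the primary question has already been answered in the negative.

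**Working it through.** **1. Reproduce the designs.** With X the number progression free at three years:

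- Stratum 1 (9.3.1: n = 77, reject if X ≥ 69): P(X ≥ 69 | 77, 0.82) = 0.0492 and P(X ≥ 69 | 77, 0.93) = 0.911. Both match the stated figures.
- Stratum 2 (9.3.2: n = 79, reject if X ≥ 73): P(X ≥ 73 | 79, 0.87) = 0.0978, within the nominal 0.10, and P(X ≥ 73 | 79, 0.95) = 0.900, matching the stated 90%.

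**2. Where the triggers come from.** Rejection becomes impossible at n − r + 1 failures, where r is the required number progression free.

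- Stratum 1: 77 − 69 + 1 = 9.
- Stratum 2: 79 − 73 + 1 = 7.

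Both triggers equal these limits, so they are aligned with the test only if every primary-analysis failure is counted.

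**3. Effect of the parenthesis.** If m primary-analysis patients have died without progression or withdrawn consent and are not counted, the trigger fires at 9 + m or 7 + m true failures. With m = 0 there is no effect.

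**4. Illustration of size.** The documents do not give the share of failures that would go uncounted, so I varied it over 10%, 20% and 30%. Inputs:

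- Accrual of evaluable patients: 11.1 per year in Stratum 1 (9.2.1); 79 / 5 = 15.8 per year in Stratum 2 (9.2.2).
- Failure probability at the null: 1 − 0.82 = 0.18 and 1 − 0.87 = 0.13.
- Failure timing: 3:1 between years 1 and 2, from the three first-year failures and one second-year failure in the historical Stratum 1 cohort (9.3.1). Section 9.3.2 gives no such split for germinoma, so using it in Stratum 2 is an assumption.

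Method: 20,000 simulated trials per scenario, with exponential inter-arrival times and failure times uniform within the year. Each failure is independently uncounted with the stated probability. The trigger fires if the 9th (7th) counted failure occurs before the 77th (79th) patient starts.

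| Share uncounted | Stratum 1: P(fires before 77 started) | Stratum 2: P(fires before 79 started) | Stratum 1: mean extra evaluable patients started, all trials |
|---|---|---|---|
| 0% | 0.88 | 0.77 | 0 |
| 10% | 0.78 | 0.66 | about 4 |
| 20% | 0.65 | 0.54 | about 8 |
| 30% | 0.49 | 0.39 | about 12 |

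Repeat runs move the probabilities by about 0.01. If the average is taken only over trials in which a full count would have fired, the extra patients are about 5, 10 and 14.

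**5. Away from the null (Stratum 1).** At 10% failure the mean delay over all trials is about 1 to 2.5 patients. At the 7% design alternative it is under 0.5, because even a full count fires in only about 5% of trials.

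**The case against.** The best defence is that the authors meant a single definition. In 9.3.1 and 9.3.2 the sentence on unevaluated patients stands between two sentences about loss to follow-up. Section 9 may therefore use that term for anyone who cannot be evaluated at three years, and thresholds equal to the test limits point the same way. This is a fair account of intent, most plausible for withdrawal and weaker for death. It does not settle the text: 8.2 keeps the three categories apart, and a rule that suspends accrual should not depend on which section the reader follows.

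Other parts of the defence stand and limit the point:

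- **Induction deaths.** A reader might infer that any treatment-related death escapes the rule. Section 9.1 excludes patients who never received reduced radiotherapy, so deaths during induction are outside the test too and create no mismatch.
- **Other routes to review.** A reader might infer that these deaths would go unseen. Section 12.2 gives the monitoring committee outcome and toxicity reports, and Section 11.3 requires expedited reporting of every death within 30 days of the last dose of a commercial agent. The trigger itself only suspends accrual pending review.
- **Section 15.12.** Its sentence "The monitoring of EFS will assess the rate of failure" might be taken as a further definition of failure. It defines nothing, and 9.3.1 itself uses EFS and PFS interchangeably for the same estimates.
- **Size.** A 10–30% share at the null means 1.8–5.4% of Stratum 1 patients (0.18 × 0.10 to 0.18 × 0.30). The documents' own experience suggests such events are few: 9.3.1 reports no censoring within two years in the historical CR/second-look and PR cohorts.

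**Conclusion.** The mismatch is real in both strata and worth correcting, but it is a fault in a monitoring rule and not in the design. Read literally, the triggers omit two kinds of patient whom the primary analysis counts as failures, and each one postpones suspension by one failure. The affected patients are those who received reduced radiotherapy and then, before three years, died without progression or withdrew consent.

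The thresholds, sample sizes, type I error, power and final decision rules are all unaffected. A reader might infer damage to the test itself; the documents do not support that.

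The size is illustrative. It rests on an assumed 10–30% uncounted share, on true failure rates at the null, and on the Stratum 1 failure timing applied to both strata. Under those assumptions the loss of trigger sensitivity is material. If the treatment performs at the design alternative, or if such events do not occur, the practical effect is negligible or nil.

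**What to change.** In 9.3.1 and 9.3.2, replace the parenthesis with: *(among patients in the primary-analysis population: progressed, died of any cause, lost to follow-up, withdrew consent, or otherwise went off study before the 3-year evaluation)*. Keep the thresholds at 9 and 7.

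The restriction to the primary-analysis population is essential. Without it, death from any cause or leaving the study would include induction deaths and patients who never received protocol treatment, and the trigger could fire while the test could still be passed. Tying the last item to going off study also keeps the count determinable in real time: a patient who is only temporarily unreachable is not counted.

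The cost is a wording amendment to two sentences, with no change to sample size, type I error or power. The only downside is that board review may come slightly earlier. Section 15.12 needs no change for this point.

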9.3.2 Stratum 2 Germinoma

The outcome for patients with localized germinoma treated with CSI is even better than the outcome for patients with NGGCT discussed above. Huh, Maity and Bamberg report 10-year PFS of 96.6% (n=32); 5-year PFS of 100% (n=39); and 5-year PFS of 88% (n=49), respectively.³³⁻³⁵ The four relapses in the Bamberg cohort were all within three years of initiating therapy. Calaminus reported an EFS rate of $97 \pm 2\%$ for 128 patients with localized germinoma treated with CSI. Thus, a similar statistical approach is justified for evaluating reduced therapy for patients with localized germinoma. The binomial distribution seems most appropriate for the design for this stratum, as again the usual time-to-event distributions, exponential, Weibull, etc. cannot be well-characterized based on the available data. The 3-year PFS rate was chosen as all failures are expected within three years of initiating therapy and we will successfully follow all patients for at least three years.

Based on the results of the SIOP-96, SFOP trial and Japanese studies, our approach will be considered acceptable if there is statistical evidence that the true, unknown 3-year PFS rate is greater than 0.87 (> 87%). Thus, a one-sided test will be used with a type I error rate of 0.10 ($\alpha = 0.10$) and 90% statistical power ($\beta = 0.10$), if the true 3-year PFS rate is 95%. Since this approach offers the potential for superior quality of life for surviving patients who are spared exposure to highly effective cranial spinal irradiation that has long term consequences for survivors, we have set the statistical power at 90%.

The sample size calculation will be based on the binomial distribution testing that the true, unknown 3-year PFS rate is at most 87% (null hypothesis: ≤ 0.87) and powered to detect that the 3-year PFS rate is really 95% (0.95). This method requires that no patient be lost to follow up within the first three years. All patients who fail to be evaluated for progression at the 3-year mark will be included in the primary analysis as failures. The Principal Investigators are committed that no patient be lost to follow up within three years of initiating treatment. East 5.4[©] was used to calculate the require sample size of 79 patients. This design will reject the null hypothesis if at least 73 patients (≥ 73) are progression free after three years. This approach was selected to minimize the number of patients with this rare

disease that would be required to address the primary study objective with statistical confidence even though considerable effort will be required to assure that no patient is lost to follow up within three years of initiating treatment. The study team is confident that this is possible.

In order for the reduced therapy approach to be considered to have sufficient merit for continued investigation, the null hypothesis must be rejected otherwise this approach will have to be reconsidered.

Due to the expected accrual rate, expected low failure rate and 3-year PFS endpoint, even one interim analysis for futility that would stop accrual early is not practical. If at any point in the trial, 7 patients are documented to have failed (progressed or been lost to follow up) before three years of follow up and fewer than 79 patients eligible for the primary analysis have begun treatment, accrual will be suspended until the COG DSMB has had the opportunity to review all data.

9.3.3 Longitudinal Modeling of Neurocognitive Function (Cognitive, Social and Behavioral)

These analyses will be conducted independently for Stratum 1 (NGGCT) and Stratum 2 (Germinoma) patients. To be included in the analyses, patients must have the 9-month baseline assessment and at least one of either the 30-month or 60-month assessments.

The ALTE07C1 standard neuropsychological and behavioral battery focuses on three cognitive domains: intelligence, attention, and memory, as well as broad domains of social, emotional, and behavioral functioning. Data for all assessments will be available as standardized t-scores. The change over time for each component of the neuropsychological testing will be estimated using Generalized Estimating Equation (GEE);⁸² with the standardized t-scores as the dependent variable and the assessment times as a covariate. For neuropsychological components for which some patients are missing data at one of the three assessments, Weighted GEE⁸³⁻⁸⁴ will be used to address the missingness under the assumption that the data are missing at random (MAR).

GEE models will be used to explore associations of changes over time with factors such as gender, age at initiation of radiation therapy, tumor location, surgical intervention, etc.

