1.0 GOALS AND OBJECTIVES (SCIENTIFIC AIMS)

1.1 Primary Objectives

1.1.1

To determine, as measured by the 3-year progression-free survival (PFS) rate and patterns of failure, whether dose and volume of irradiation can be safely reduced to 30.6 Gy whole ventricular field irradiation (WVI) plus 23.4 Gy primary site boost instead of 36 Gy craniospinal irradiation (CSI) plus primary site boost in the subgroup of children and young adults (ages 3 to ≤ 21 years) with localized non-germinomatous germ cell tumor (NGGCT) who have a magnetic resonance imaging (MRI) and tumor marker criteria (CSF and serum) for confirmed complete response (CR) or partial response (PR) to induction chemotherapy and negative serum and cerebrospinal fluid (CSF) tumor markers OR in patients who have less than a PR after induction chemotherapy with negative tumor markers who undergo a second-look surgery and are found to have only mature teratoma, residual scar or fibrosis and fit the definition of CR/PR after second-look surgery.

1.1.2

To determine, as measured by the 3-year PFS rate and patterns of failure, whether simplified chemotherapy followed by dose-reduced radiation therapy is effective for treating children and young adults (ages 3 to ≤ 21 years) with localized primary central nervous system (CNS) germinoma who present with serum and/or CSF human chorionic gonadotropin-beta (hCG β) ≤ 50 mIU/ml.

1.1.3

To prospectively evaluate and longitudinally model the cognitive, social, and behavioral functioning of children and young adults who are treated with reduced radiation dose and volume of irradiation in Stratum 1 (NGGCT) and with dose-reduced radiation therapy in Stratum 2 (Germinoma) using the ALTE07C1 protocol. This objective will be assessed independently for the two strata.

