2.1.2 Role of Chemoradiotherapy

Radiation therapy (RT) plays an important role in the treatment of NGGCT; however, regimens that use RT alone have only achieved 5-year OS rates of 20%-40%, and most patients relapse within 18 months of diagnosis. ^{2,25-27} Combined modality therapy including chemotherapy and RT is considered the current standard of care. Since CSI and whole brain irradiation (WBI) are associated with significant late effects, minimizing exposure to RT by stratifying patients according to risk of disease progression after combined modality therapy has been the hallmark of recent international clinical trial designs. ¹⁰⁻¹² COG Study ACNS0122 utilized 36 Gy CSI with IFR to 54 Gy following 6 cycles of induction chemotherapy, and this resulted in a 2-year PFS and OS of 84.4 +/- 4% and 93 +/- 3%, respectively. ²⁸⁻³¹ In the Société Internationale d'Oncologie Pédiatrique (SIOP) CNS GCT-96 trial (n=172), those patients with localized disease (n=135) received 4 courses of chemotherapy (cisplatin, ifosfamide and etoposide) followed by IFR to 54 Gy. At a median follow-up of 39 months, the reported PFS for the patients with localized disease was 69 ± 5%. There were 33 relapses in this group including 18 that were local, 3 that were distant and 12 that were combined relapses. This data supports the use of a more localized field of radiation as the failures were predominantly local and distant spinal relapse were quite rare. ³² The Japanese GCT study group treated "intermediate prognosis" patients with 5 cycles of carboplatin and etoposide followed by WVI to 30.6 Gy and IFR to 50 Gy and showed a 10-year PFS and OS rates of 81.5% and 89.3%, respectively. ^{8,9} Patients with predominantly malignant germ cell tumor elements formed the Japanese "poor prognosis group" and were treated with 3 cycles of ifosfamide, cisplatin, etoposide and CSI. They received an additional 5 cycles of the same chemotherapy after CSI. The 10-year PFS and OS rates were 58.8% and 62.7%, respectively. ^{8,9}

Given the excellent results reported from the Japanese cooperative group, the SIOP CNS GCT-96 and COG ACNS0122 trial, the combination of induction chemotherapy followed by WVI with IFR to the primary site appears to be a very promising approach for a select group of NGGCT patients.

2.1.3 Rationale for Choosing Patients with CNS NGGCT who achieve a Complete or Partial Response to Induction Chemotherapy as a Subgroup for Reducing Radiation Dose and Volume

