Assessing neurocognitive function for patients treated on ACNS1123 will be considered feasible unless statistical evidence develops that fewer than 80% of patients who are eligible and evaluable for assessing primary objectives 1.1.1 or 1.1.2 and who are failure free at three years post initiation of therapy can be expected to have both 9-month and 30-month neurocognitive assessments on ALTE07C1. This rate of success will ensure that longitudinal modeling of neurocognitive function will provide viable historical controls for subsequent COG trials of these diseases. The rate of also achieving 60-month (5-year) neurocognitive assessments is not considered for monitoring feasibility, as the total study duration is only expected to be approximately seven years.

The statistical criteria for monitoring neurocognitive evaluations are based on a one-sided test ($\alpha = 0.025$) that the true, unknown, success rate is at least 80% ($\geq 80\%$) with 80% statistical power to detect that the success rate is 65%, which would be unacceptable. Assuming a binomial distribution, EAST5 was used to calculate the two stopping boundaries. If within a stratum, 9 (≤ 9) or fewer of the first 23 patients evaluable for feasibility (39.1%) have both 9 and 30 month evaluations (i.e. patients who are eligible and evaluable for assessing the primary objective and are more than 30 ± 4 months from

diagnosis), we will recommend to the COG DSMB that consideration be given to closing the stratum. The second boundary for recommending closing the stratum will be if 28 or fewer (≤ 28) of the initial 45 patients evaluable for feasibility (62.2%) enrolled in that stratum have both 9 and 30 month evaluations (i.e. patients who are eligible and evaluable for assessing the primary objective and are more than 30 ± 4 months from diagnosis). Otherwise accrual to the stratum will continue until the full cohort of patients required to address the primary objective assessing the 3-year progression-free survival rate has been achieved.

Our ability to address the secondary objectives depends upon whether the proposed treatment regimen is effective or not. Secondary objectives will be reported descriptively and as exploratory. Other than reports requested by the COG DSMB, secondary objectives will only be analyzed at the end of the trial.

1. The first secondary objective is to provide Kaplan-Meier estimates of distributions of PFS and overall survival for NGGCT patients.

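### The neurocognitive analysis set drops patients seen only at 9 months before Weighted GEE is applied, so the visit means, and to a lesser degree the change, are biased if return depends on the 9-month score

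*Combined protocol and SAP*

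**What the plan says.** Objective 1.1.3, listed as primary, is "To prospectively evaluate and longitudinally model the cognitive, social, and behavioral functioning of children and young adults". Section 9.3.3 gives the analysis, run separately in each stratum. To enter, "patients must have the 9-month baseline assessment and at least one of either the 30-month or 60-month assessments". Change in each component is estimated by GEE, with the standardized score as outcome and assessment time as covariate. Weighted GEE under MAR is then prescribed: "For neuropsychological components for which some patients are missing data at one of the three assessments". A patient with only the 9-month score lacks two assessments, and so falls outside both the analysis set and the stated use of weighting.

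Section 9.3.3 does not say on which patients the weight model is fitted or which predictors it uses. It plans no sensitivity analysis and no comparison of returners with non-returners.

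Section 9.1 monitors completion. It concerns evaluable patients "who are failure free at three years post initiation of therapy can be expected to have both 9-month and 30-month neurocognitive assessments", with a target of 80%. It adds: "The rate of also achieving 60-month (5-year) neurocognitive assessments is not considered for monitoring feasibility". The purpose given is that "longitudinal modeling of neurocognitive function will provide viable historical controls for subsequent COG trials of these diseases".

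**The concern.** Everyone admitted to the analysis has returned at least once. Within that set there is no information about the chance of never returning, so no weight fitted there can stand in for those who did not come back. Yet MAR permits return to depend on the observed 9-month score, and it is the 9-month-only patients who show whether it does. The inclusion rule discards what the missing-data method needs.

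The rule also serves no modelling purpose. With score as outcome and time as covariate, a patient with one assessment can contribute.

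If children with lower 9-month scores return less often, the reported levels would be too favourable and the decline slightly overstated. Later trials could inherit both errors if they use these models as controls.

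**Working it through.** **Inputs.** From the documents: the inclusion rule, GEE and Weighted GEE under MAR (Section 9.3.3); visits at 9, 30 and 60 months (Section 7.2); 77 and 79 evaluable patients (Section 9.2.3). The documents state no figure for this bias, so there is none to reproduce. Assumed: SD 10; true means 50, 48 and 46 at the three visits; correlation 0.7 (range 0.5-0.85); 10% or 20% never returning; log-odds of never returning rising 0.5 or 1.0 per SD lower 9-month score.

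**Formula.** Let d = E[Y9 | returned] − E[Y9], and let b be the slope of the later score on the 9-month score (equal to the correlation when SDs are equal). In the plan's set the biases are:

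- 9-month mean: d
- later mean: b·d
- change: (b − 1)·d

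If return is unrelated to score, d = 0 and all three vanish. If b = 1, expected change does not depend on the 9-month score; the change is then unbiased, but the visit means are not.

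**Results at b = 0.7, true change −2.00.** The values of d and the last column are from simulation with 2,000,000 patients per scenario.

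| Never return | Log-odds per SD | 9-month bias, d | 30-month bias, 0.7d | Change bias, −0.3d | Simulated change |
|---|---|---|---|---|---|
| 10% | 0.5 | +0.49 | +0.34 | −0.15 | −2.14 |
| 10% | 1.0 | +0.90 | +0.63 | −0.27 | −2.27 |
| 20% | 0.5 | +0.96 | +0.67 | −0.29 | −2.29 |
| 20% | 1.0 | +1.73 | +1.21 | −0.52 | −2.52 |

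Over correlations 0.5-0.85 the change is too negative by 0.07-0.45 points at 10% and 0.14-0.86 at 20%.

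**Against sampling error.** With 77 patients at correlation 0.7, the SD of the estimated change is about 0.93 (10%) or 0.98-0.99 (20%). The bias is then 0.14/0.93 = 0.15 to 0.27/0.93 = 0.29 SE, or 0.29/0.98 = 0.30 to 0.52/0.99 = 0.53 SE. A nominal 95% interval covers 93-94% or 91-93%.

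**Does weighting repair it?**

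1. In a three-visit run where 60-month absence depended on the 9-month score, weights fitted inside the plan's set left the 30-month change at −2.15 to −2.53 against −2.00.
2. Including all 9-month patients, with inverse-probability weights from the 9-month score, gave −2.00 for the 30-month change in every two-visit scenario.
3. For the 60-month visit the choice of predictors matters. When 60-month absence depended on the 30-month score (true 9-to-60-month change −4.0), weights using only the 9-month score gave −3.28 to −3.68. The plan's set gave −4.14 to −4.53. Sequential weights using all previously observed scores gave −3.98 to −4.04.

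**Two partial repairs that make the 30-month change worse (correlation 0.7).**

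- Keeping the plan's set but weighting only the later rows, with a model fitted on all 9-month patients: −2.49 to −2.91 (10%) and −2.96 to −3.73 (20%).
- Adding 9-month-only patients to an unweighted GEE with independence working correlation: −1.65 to −1.36 and −1.33 to −0.79.

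**The case against.** The strongest defence is that the effect is small and rests on assumptions. Section 9.3.3 targets change, where the bias is at most about half a standard error in the main scenarios. No test depends on it. SD, correlation, never-return rate and score-dependence all come from outside the documents. ALTE07C1 enrolment is mandatory (Section 3.2.5), completion is monitored (Section 9.1), patients off therapy are still followed (Section 8.1), and the investigators commit to losing nobody within three years (Sections 9.3.1 and 9.3.2). These points stand as limits on size. They reduce how many are missing but do not adjust for who is missing, and follow-up for progression does not ensure attendance for testing.

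A second objection also stands in part: the remedy can do harm. A 60-month weight model that ignores the 30-month score was worse than the plan's set in 7 of 8 settings examined. At 10% loss, 77 patients yield about 8 non-returners. With age, sex and location added to the weight model, about 24% of simulated cohorts showed near-separation and the RMSE gain for the change largely disappeared (0.945 against 0.942, and 0.977 against 1.005). The weight model must therefore be sequential and small. Nor do such weights by themselves cover absence driven by recurrence, for instance when Section 8.2 takes a patient off study on entering another COG therapeutic trial.

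Three stronger readings are tempting but not supported:

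- **That over a third of patients may never return.** The second monitoring boundary is 28/45 = 62.2%, so 29/45 = 64.4% passes and up to 16/45 = 35.6% could be incomplete. That share also counts patients with no 9-month score and patients seen at 9 and 60 months, whom the analysis keeps.
- **That the estimated change must be biased whenever return depends on score.** It is not if b = 1.
- **That later trials will compare levels.** Section 9.1 speaks only of longitudinal modelling as a source of controls.

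**Conclusion.** The point holds. The stated inclusion rule gives biased visit means under the plan's own MAR assumption whenever return depends on the 9-month score, and a smaller bias in the change unless expected change is unrelated to that score. Under the central assumptions the levels are off by up to about 1.7 points at 9 months and 1.2 at 30 months, and the change by 0.1-0.5. The 20% loss is on the high side. The direction assumes that lower scorers return less often. This does not invalidate objective 1.1.3 and does not touch the PFS tests. It is a modest, avoidable bias in a primary-objective analysis, and it matters most for the levels.

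**What to change.** Replace the inclusion sentence in Section 9.3.3 with:

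> All eligible, evaluable patients with a 9-month assessment are included. Weights are the inverse of the cumulative probability of being observed, from visit-specific models fitted sequentially on all of these patients alive at that visit, using all previously observed scores (the 9-month score for the 30-month visit; the 9-month and, where observed, 30-month scores for the 60-month visit) and, where numbers allow, a small number of prespecified baseline factors.

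Change the set and the weight model together; either alone can increase the bias. State explicitly how a patient seen at 60 but not at 30 months is weighted. Such patients need their own 60-month observation model, and their one-visit weights should not be mixed with cumulative weights for the others.

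Also:

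- Report visits missed because of death separately, not as ordinary missed visits. They should be few before 30 months: for the preceding trial, with a broader population, Section 2.1.2 reports that "this resulted in a 2-year PFS and OS of 84.4 +/- 4% and 93 +/- 3%, respectively".
- Compare 9-month scores and baseline factors of returners and non-returners.
- As sensitivity analyses, give a likelihood-based mixed model using all available assessments (which also brings in patients without a 9-month score, and extrapolates visits after death), and the plan's two-assessment set.

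**Cost.** SAP wording and minor programming on data already collected. With weights from the 9-month score alone and 77 patients, the RMSE of the change moves only from 0.94/0.97 to 0.93/0.96 at 10% loss and from 1.03/1.11 to 0.99/1.06 at 20% (log-odds 0.5/1.0). The main gain is in the levels: the 9-month RMSE falls from 1.29/1.47 to 1.14 at 10%, and from 1.59/2.10 to 1.13-1.15 at 20%.
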